Conservative treatment of the Epicondylitis or osis is recommended as the initial strategy by most authors. This strategy includes identification and correction of possible etiological factors, and a symptom-related approach. Generally, the initial treatment consists of a multifactorial approach that may include a combination of rest (complete or modified activity), medication (NSAIDs for Epicondylitis), stretching and strength training⁹.

Intense Therapeutic Ultrasound (ITU) is a novel potential treatment for CET Tendinosis. ITU is a highly focused ultrasound wave that delivers enough energy intensity to disrupt soft tissues within a controlled up to 1 mm³ volume, while sparing surrounding tissue structures. Much like a laser is formed by focusing light to concentrate energy over a small area, ultrasound can emit sound waves that can propagate through tissues to deliver selective thermal coagulative changes while leaving the surrounding tissue unaffected.^{11,12,13}

ITU has been used clinically for treating the facial soft tissue for the past decade and it has received FDA approval for non-surgical brow and submental lifting. Over 300,000 treatments have been performed with this technology. Clinical studies in 2005/2006 (IRB#'s 05-06-032, 1253-014) using intense therapeutic ultrasound (ITU) on facial soft tissue whereby the energy is focused underneath the skin tissue to achieve controlled coagulative necrosis (~1 mm³) were performed. Seventy subjects were involved in the studies and 84% of subjects showed an improvement in facial lifting with no significant pain, erythema,

inflammation, or scarring^{11,12}. Slight edema and erythema were noted on some subjects, all resolving within 30 minutes after treatment.

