Subjects will receive conservative standard of care treatment plus two ITU treatments (week 0 and week 4) on the affected CET (figure 2) using the ultrasound therapy device. Treatments will be up to 10 minutes in duration. A 2, 4, and 8 week follow up period will be included to monitor the effects of the therapy post treatment. A 12 and 24-26 week telephone assessments for the primary objectives will also be included. Telephone assessments will consist of the subjects answering the survey questions over the phone.

Subject self-assessments will be conducted before the treatment phase and during the follow-up period. Physical exams will be completed by a physician. Physical therapy will be completed by a therapist. ITU treatment and diagnostic ultrasound will be performed by Guided Therapy personnel as shown in the full schedule of events (Appendix 1).

[figure not shown]

Figure 2: Treatment Area

SELECTION OF SUBJECTS**Planned number of subjects**

The study population will consist of up to 25 subjects with unilateral CET tendinosis defined as pain lasting more than 3 months with little or no improvement following conservative standard of care alone.

The selection of suitable subjects will be made according to the inclusion and exclusion criteria described in the following sections.

Inclusion Criteria

1. Subjects who are in general good health and are willing to cooperate and participate by following study requirements for the duration of the study, and to report any adverse symptoms immediately;
2. Subjects who have provided written and verbal informed consent;
3. At time of enrollment subjects are between the ages of 21 and 65 years
4. Subjects literate in English and able to complete all patient self-assessment questionnaires;

5. Subjects is willing to refrain from beginning any additional treatment during the duration of the study;
6. Subjects is willing to refrain from changing physical activity during the duration of the study;
7. Subjects diagnosed with unilateral CET tendinosis defined as pain lasting more than 3 months with little or no improvement following conservative standard of care alone.
8. Subjects with BMI ≤ 35 or at the discretion of the PI.
9. Subjects must be able to sit in a chair with their arm on an appropriate table for the treatment and diagnostic ultrasound imaging.
10. Subject must be able and willing to complete the at home therapy regimen.

Exclusion Criteria

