Social Hx: Frequently found those involved in racquet sports.

Medications: non-steroidal anti-inflammatory medications and corticosteroids.

Pain: measured on the VAS scale; note activities that increase symptoms, decrease symptoms, and the location of symptoms.

Examination protocol is simple and will consist of the following:

- a. Skin examination (note any rashes, lesions, areas of skin irritation over the lateral elbow region)
- b. Palpation over the lateral epicondyle of affected side, note presence of tenderness to palpation vs. no tenderness to palpation
- c. Check range of motion of elbow in flexion, extension, pronation, and supination (may use normative template data that is in EMR under elbow exam)
- d. Check provocative tests for lateral epicondylitis and note whether or not these elicit pain that refers into the common extensor tendon. The 2 provocative tests will be: 1. Resistance to active wrist extension. 2. Resistance to active middle finger extension

Ultrasound Imaging

Ultrasound images will be collected from test sites on both the affected and unaffected CET using the Spark® High Frequency Ultrasound System. CET tendon thickness, homogeneity and gross assessment of the CET tendon and surrounding tissue will be conducted.

Assessment of Safety

Recording of Adverse Events or any other significant event will take place at all visits. Adverse events will be monitored throughout the study. (Appendix 5)

ASSESSMENTS AT EACH VISIT

An overview of the assessments to be conducted at each study visit are presented in a Table in Appendix 1.

Subjects will be treated at Visit 1 and Visit 3. Imaging will occur, before the treatments, and at visits 2, and 4. The PRTEE questionnaire will be administered, prior to the first treatment at visits 1 and 3, and at visits 2, and 4. An additional telephone follow-up, where answers to the questionnaires will be recorded, will occur at 12 and 24 weeks post treatment one (1) per the schedule in Appendix 1.

The study will last approximately two (2) months with a follow-up phone call at three (3) and six (6) months.

Visit 0 (Recruitment): Screening and Enrollment

1. Candidate subjects will read an informed consent (which includes a confidentiality agreement) and will sign (along with a witness) after all questions about the study have been answered. Individuals will be issued a temporary screening number.
2. Eligibility paperwork will include documentation of pregnancy status and pertinent medical history.

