
If a subject meets all the inclusion/ exclusion criteria, they will be enrolled onto the study, issued a subject number and an X-ray will be scheduled.

Visit 1 and 3: (Weeks 0 and 4) Study treatments

1. Record AEs, con meds and other events
2. Administer PRTEE-A questionnaire (Appendix 2)
3. Subject self-assessment questionnaire (Appendix 3)
4. Focused Physical Evaluation
5. Diagnostic Ultrasound images taken
6. ITU treatment, and VAS assessment of treatment tolerability.
7. Physical Therapy will be performed as described (Appendix 4 – Visit 1 only)
8. Home Cold Pack & Stretching Program review and Log (Appendix 6-A and 6-B)

Visit 2, and 4: (Weeks 2 and 8) Diagnostic Ultrasound, Self-Assessments, Physical Examination

1. Record AEs, con meds and other events;
2. Administer PRTEE-A questionnaire (Appendix 2)
3. Subject self-assessment questionnaire (Appendix 3)
4. Diagnostic Ultrasound image taken;
5. Home Cold Pack & Stretching Program review and Log (Appendix 6-A and 6-B)

Phone/Online Interviews at 3 and 6 months post treatment

1. Record AEs, con meds and other events;
2. Follow-up phone interview PRTEE-A verbally administered (Appendix 2).
3. Subject self-assessment questionnaire (Appendix 3)

STUDY TREATMENT

ITU will be performed by a trained technologist, using a clinical prototype (Ulthera FDA cleared in Sept. 2009) GEN II or GEN III designed Guided Therapy Systems, LLC. Mesa, AZ USA (Appendix 7-A).

Subjects will be treated seated with their arm resting on a structure that is comfortable for the subject and technologist. Transdermal application of ITU therapy: An average energy up to 3 joules (0.5 to 3 J) will be administered to the affected CET tendon longitudinally until the maximum number of lines (12) are reached. Each line will include individual thermal zones, less than 1 mm³ in volume, centered at a depth between 2 – 6 mm, up to 2 mm apart (figure 3).

[figure not shown]
[figure not shown]

Figure 3. Zone pitch, and depth. Tendo

Treatment pattern:

Acoustic Coupling Gel will be applied every 3-5 lines.

Figure 3-1. Zone pitch, and depth.

The study treatment will be a 10 minute session using the ultrasound therapy device with coupling gel. Subjects will be treated seated with their arm resting on a structure that is comfortable for the subject and technologist.

DIAGNOSTIC ULTRASOUND IMAGING

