Diagnostic Ultrasound Imaging will be performed by a trained Sonographer using the Spark® Imaging System, manufactured by Ardent Sound, Inc., Mesa, AZ USA (Appendix 7-B)

Subjects will be imaged seated with their arm resting on a structure that is comfortable for the subject and sonographer.

PolySonic® or AquaSonic® Gel will be applied by the sonographer as required to maintain adequate acoustic coupling. (Appendix 7-C)

1

[figure not shown]
Images will be preserved with the following notations:

- Protocol ID
- Right vs. Left CET Tendon
- Treated vs. Untreated

Long Axis and Short Axis (if necessary) images will be stored at the Sonographer's discretion, to demonstrate and track the applicable anatomy/pathology in the peri-CET area.

Sonographer will also measure the thickness of the CET tendon in each applicable image.

Sonographer will scan the contralateral CET tendon in the same manner noting the change in the tendon (Right v. Left) and (Treated v. Untreated).

Common Extensor Tendon
Figure 4: representative long axis ultrasound images

Outcome measures

Subjects will complete subject reported outcome measures at 0, 2, 4, 8, 12, and 24 weeks and will undergo a focused physical examination and diagnostic ultrasound at 0, 2, 4, and 8 weeks. Adverse events will be recorded at each visit. Treatment tolerability will be assessed immediately after each treatment using the Visual Analog Scale for Pain (VAS) or Universal Pain Assessment Tool (Appendix 3-B). The VAS will be used for 2 different assessments: 1. Pain related to physical activity of the symptomatic arm before treatments and at follow-up visits and phone surveys. 2. Pain tolerance of the therapy treatment. Each of these assessments will be documented and evaluated separately.

Aim 1: reported outcomes

The principal aim of this study is to assess the efficacy of treatment and time course of response to treatment using validated subject reported outcome measures assessing pain, function and level of activity. Subjects will complete validated subject reported outcome questionnaires assessing pain, function and level of activity prior to initiating treatment and at

0, 2, 4, 8, 12, and 24 weeks after starting treatment (Appendix 2 and 3A).

Clinical Pain and Treatment Tolerance will be assessed using the Visual Analog Scale for Pain (VAS) or Universal Pain Assessment Tool (Appendix 3-B).

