Recording of adverse events will take place at all visits (see adverse event reporting form Appendix 5). Adverse events will be monitored throughout the study.

A treatment will not be administered if there is residual pain/discomfort experienced by the subject from the previous treatment.

ACCOUNTABILITY

Treatment administered to the subjects will be documented by the operator and tracked on the Case Report Form (CRF).

BREAKING THE CODE IN AN EMERGENCY

Treatment codes and allocation of treatment per subject will be accessible by the Principal Investigator of the study.

SAFETY MONITORING**ADVERSE EVENT**

An adverse event (AE) is any untoward medical occurrence in a subject, whether or not related to study product or study procedures. Adverse events include any occurrence that is new in onset, an exacerbation of a pre-existing condition and clinically significant laboratory values.

Exceptions

The following medical occurrences will not be reported as AEs;

- Pre-treatment Adverse Events; Any medical occurrence that occurs after informed consent, but before first administration of ITU treatment or first study procedure is considered as medical history and only recorded as an AE if it worsens during the study.
- Pre-existing medical condition; Events that occur with comparable frequency and severity to the subject's baseline condition are reported as medical history, not AEs unless they become exacerbated during the study.
- Pregnancy; This is not an AE however the PI must report any pregnancies to The Guided Therapy and the Institutional Review Board (IRB) for advice regarding the appropriate course of action.

Study Specific Expected Adverse Event

The following AEs are expected due to the use of these study products and/or procedures and for this specific study, they will not be regarded as AEs;

- Transient erythema may be expected as a result of the study treatment which is expected to subside after a few hours. This will not be recorded as an AE unless persistent after 24 hours.
- Subjects may experience mild-moderate tingling, warming, pain or discomfort during the study treatments. These will not be recorded as AEs unless persistent after 24 hours or if they increase to severe/unbearable sensations.

The following AEs may be expected due to the use of these study products and/or procedures and for this specific study, they will be regarded and recorded as AEs;

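### The 24-hour rule for counting treatment reactions as adverse events has no scheduled observation behind it, and no recorded skin check follows either ITU session

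*Protocol*

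**What the plan says.** **The AE rule.** In the Protocol, Study Specific Expected Adverse Event, transient erythema is expected and is handled so: "This will not be recorded as an AE unless persistent after 24 hours". For tingling, warming, pain or discomfort of mild to moderate degree: "These will not be recorded as AEs unless persistent after 24 hours or if they increase to severe/unbearable sensations". A burn or high skin irritation response from operator error is listed separately. It is an AE whatever its duration.

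**The exposure.** Study Outline: "two ITU treatments (week 0 and week 4) on the affected CET".

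**The skin check.** Physical Examination, item (a): "Skin examination (note any rashes, lesions, areas of skin irritation over the lateral elbow region". Under Outcome measures, subjects "will undergo a focused physical examination and diagnostic ultrasound at 0, 2, 4, and 8 weeks". Appendix 1 shows the same four times.

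**The order on treatment days.** In the list for Visits 1 and 3, AE recording is step 1, the focused physical evaluation is step 4, and step 6 is "ITU treatment, and VAS assessment of treatment tolerability". Steps 7 and 8 are physical therapy (Visit 1 only) and review of the home program.

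**The follow-up visits.** The heading reads "Visit 2, and 4: (Weeks 2 and 8) Diagnostic Ultrasound, Self-Assessments, Physical Examination". None of the five numbered items beneath it is a physical examination.

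**The concern.** Two kinds of reaction are at issue, and each lacks a different observation.

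- Erythema and mild-to-moderate sensations are classified by their state at 24 hours. Nothing is scheduled at or near that time, so the rule has to be applied from whatever the subject volunteers or remembers.
- Burns and high skin irritation need no duration test. However, the examination that would document them is listed before the exposure, and no recorded look at the skin follows it.

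The study has safety and tolerance among its objectives, and the SAP describes only pain and PRTEE summaries. The safety conclusion therefore rests on the AEs that reach the case report form. If reactions can clear before anyone asks, a favourable AE table may partly reflect when the site looked.

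**Working it through.** The protocol states no figure to reproduce here; the check is schedule arithmetic plus a comparison of sections.

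**1. Time to the next scheduled contact**

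Inputs: ITU at weeks 0 and 4 (Study Outline); examinations at weeks 0, 2, 4 and 8 (Outcome measures, Appendix 1); AE recording at those visits and at the telephone interviews at 12 and 24 weeks (Assessments at Each Visit).

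Interval = (week of next contact − week of session) × 7 days.

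| Session | Next examination | Next AE recording | Interval |
|---|---|---|---|
| 1 (week 0) | week 2 | week 2 | (2 − 0) × 7 = 14 days |
| 2 (week 4) | week 8 | week 8 | (8 − 4) × 7 = 28 days |

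No contact is scheduled between a session and the visit shown. With up to 25 subjects and two sessions each, this applies to up to 25 × 2 = 50 sessions. The intervals are nominal, because no visit windows are given.

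**2. What the existing safeguards record**

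| Provision | Duration past 24 h? | Skin state near 24 h? |
|---|---|---|
| VAS immediately after ITU (Outcome measures) | No | No, pain only |
| Willingness to report symptoms at once (inclusion criterion 1) | Only if volunteered | Only if volunteered |
| AEs monitored over the whole study (Aim 3) | No method or time named | No method or time named |
| Current pain and maximum pain since last treatment (Aim 3) | No, intensity only | No |
| Home log (Appendix 6-B) | No, exercise and massage sets only | No |

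**3. Which events can be lost**

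A reaction that clears within 24 hours and stays mild to moderate is not an AE by the protocol's definition, so missing it is no undercount. The exposed group is reactions that last beyond 24 hours, resolve before the next visit, and are neither reported nor recalled. Burns and high skin irritation that heal before the next visit share the dependence on report or recall, unless the operator notes them at the session.

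**4. How incomplete capture would act (assumed values, not estimates)**

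The documents give neither a reaction risk nor a capture rate. Let p be the per-subject risk of a reaction that qualifies as an AE and c the chance that it is recorded. The chance that none is recorded in 25 subjects is (1 − p·c)^25.

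| p | c = 1 | c = 0.5 | c = 0.25 |
|---|---|---|---|
| 5% | 0.95^25 = 0.28 | 0.975^25 = 0.53 | 0.9875^25 = 0.73 |
| 10% | 0.90^25 = 0.07 | 0.95^25 = 0.28 | 0.975^25 = 0.53 |

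These values show only the direction and the sensitivity at this sample size.

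**5. Visit 2 and 4 list**

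The list's own heading, Outcome measures and Appendix 1 all include a physical examination at weeks 2 and 8. The numbered items do not. Three places agree and one differs.

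**The case against.** The strongest reply is that recall is not the only route. Subjects are selected for willingness to report symptoms promptly, AEs are to be monitored throughout, follow-up asks for the worst pain since treatment, and residual pain or discomfort must be considered before a further treatment. A trained technologist works at the treated skin during the session and reapplies gel every few lines, and at Visit 1 physical therapy is listed after ITU. All of this stands and makes complete loss of a burn less likely. It does not supply a duration, a skin state near 24 hours, or a recorded post-exposure check. It is also fair that the order of examination and ITU is inferred from the step numbers; no sentence states it.

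Three stronger readings are tempting, and the documents do not support them.

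- A reader might infer that AE counts are certain to be biased low. With the safeguards above and no rate in the documents, only a possible downward bias follows.
- A reader might set the 24-hour threshold against the Introduction's statement "Slight edema and erythema were noted on some subjects, all resolving within 30 minutes after treatment" and call the threshold far too lenient. That experience is from facial soft tissue. For this study the protocol expects erythema to subside after a few hours, and where to set the threshold is a separate matter of definition.
- A reader might infer from the Visit 2 and 4 list that the skin is never examined after session 2. That requires ignoring the list's own heading, Outcome measures and Appendix 1. It is an inconsistency to reconcile.

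**Conclusion.** The point holds as a gap in ascertainment that is cheap to close. The protocol has a 24-hour classification rule but schedules no observation that can feed it: the next contact is nominally 14 days after session 1 and 28 days after session 2. No recorded skin check follows the exposure, which also matters for burns and high skin irritation even though they need no duration test. AE counts may be biased low. The size cannot be stated, because the documents give neither reaction rates nor capture rates.

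The conclusion assumes that the Visit 1 and 3 steps are carried out in numbered order and that visits fall on their nominal weeks. It does not call the 24-hour threshold or the treatment schedule into question. The missing item in the Visit 2 and 4 list is a separate inconsistency.

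**What to change.** 1. **Visits 1 and 3.** After ITU and before the subject leaves, repeat existing skin examination item (a) and record it on the CRF. This captures burns and immediate irritation; it cannot serve the 24-hour rule.
2. **Home log (Appendix 6-B).** Add a day-after-treatment entry with two fields: skin change still present at 24 hours (yes/no), and treatment sensation or pain still present at 24 hours (0–10). Key it to each subject's treatment dates, because the present log carries fixed calendar dates. Review it at the next visit. The investigator classifies the AE from the entry and asks the subject directly if it is blank.
3. **Visit 2 and 4 list.** Reconcile the numbered items with their heading, Outcome measures and Appendix 1.

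The cost is slightly more form work at and after each session, and possibly a few more minor AEs on record. No visit is added. The day-after entry remains self-report, but it is made close to the time the rule refers to.
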